- 1. For cohorts requiring 3 or more evaluable subjects, if only 2 evaluable subjects are available for assessment (all others drop out), and neither subject has had a treatment-related or possibly-related toxicity greater than CTCAE Grade 1, then 2 subjects will be considered sufficient for decision-making
- 2. If the first 2 subjects in a cohort have a DLT, further enrollment to the study will be temporarily suspended and the Bayesian model will be updated with this new information. If the Bayesian model supports enrolling the next cohort at the dose level where 2 DLTs occurred, or at a higher dose level, the relevant data and rationale will be discussed and agreed upon by sponsor and the Investigators of the escalation phase. If sponsor and the Investigators agree that it is medically appropriate to enroll an additional cohort at the dose level where 2 DLTs occurred or at a higher dose, the data and rationale supporting this decision will be documented.

Following the principle of escalation with overdose control (EWOC), after each cohort the recommended dose will be the one with the highest posterior probability of the DLT rate falling in the target toxicity interval [0.166, 0.333) among the doses fulfilling EWOC. Per EWOC, it should be unlikely (< 25% posterior probability) that the DLT rate at the dose will exceed 0.333.

For further understanding of the safety, tolerability, and PK of VX 984 in combination with PLD, additional cohorts of subjects may be enrolled at preceding dose levels, or to intermediate dose levels before or while proceeding with further dose escalation. The maximum planned dose of VX-984 is 2000 mg during escalation, however, higher doses up to 3000 mg may be allowed depending on the observed safety, PK, and PD, and based on recommendation of the BLRM.

After repeating the above steps, the dose escalation of VX-984 will continue with a constant dose of PLD at 40 mg/m^2 until MTD is achieved.

If a dose of VX-984 is not tolerated with PLD at 40 mg/m², then the VX-984 dose may be reduced by up to 50% with a constant dose of PLD at 40 mg/m² or the dose of PLD will be reduced by 25% (30 mg/m²) or lower with a constant dose of VX-984. These doses will be explored in subsequent cohorts at the discretion of the Investigators and sponsor. If daily dosing of VX-984 for 3 days after PLD is not tolerated during initial dose escalation, less frequent dosing of VX-984 may be explored in subsequent cohorts.

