# 8.1.2.1.7 Subject Evaluability

All subjects who meet the eligibility criteria and receive at least 1 dose of VX-984 will be evaluable for safety.

In order for subjects to be evaluable for dose escalation decisions:

- Subject must receive PLD on Day 1 and receive all 3 doses of VX-984 within 5 days (Days 2 to 6) with the first dose of VX-984 on Day 2; or
- The subject must have had a DLT during Cycle 1.

Subjects who do not fulfill at least 1 of the 2 above criteria will not be evaluable for dose escalation decisions and will be replaced.

In the event of a Grade 3 or higher elevation in ALT or AST, follow-up laboratory assessments should be performed every 48 to 72 hours until reduced to Grade 2 or lower.

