## 8.1.2.2 Part B

During each cycle, subjects will be administered PLD on Day 1, and VX-984 will be dosed on Days 2 to 4 of a 28-day cycle unless in Part A the number of days was decreased due to tolerability. Treatment Period assessments are listed in Table 3-3. Approximately 40 subjects will receive VX-984 with PLD at the MTD or lower, as determined during the dose escalation phase.

Upon completion of the first cycle of treatment for at least 10 subjects within Part B, if the observed DLT rate exceeds 33.3%, the BLRM will be re-run to confirm that the estimated MTD still satisfies the overdose criteria of the model. If the dose fails to satisfy the criteria, a

change to the dose under study may be made according to the BLRM recommendation after review of the clinical data.

Subjects will continue to receive treatment until disease progression, unacceptable toxicities, or withdrawal of consent. Subjects will be evaluated by CT scans at the end of every 2 cycles for the first 6 cycles and every 2 to 3 cycles thereafter (see Table 3-3). If in the opinion of the Investigators, subjects may benefit with continued treatment with PLD and VX-984, subjects may continue to receive treatment beyond the total exposure of 550 mg/m² PLD. If there is evidence of progressive disease as determined using RECIST 1.1, treatment will be discontinued. In addition, subjects will be evaluated by transthoracic echocardiogram at baseline and at the end of every 2 cycles (see Table 3-3).

All subjects who meet the eligibility criteria and are administered at least 1 dose of VX-984 will be evaluable for safety. Subjects who meet the eligibility criteria, are administered at least 1 cycle of study drug, and have a baseline scan will be evaluated for efficacy. For subjects requiring palliative radiotherapy, irradiated lesions will be evaluable for progression, not response.

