# 12.2 Analysis Sets

#### For Part A:

• The DLT Evaluable Set is defined as all subjects in the Safety Set of Part A who either meet the minimum exposure criterion and have sufficient safety evaluations (as determined by the Investigators and sponsor), or have had a DLT during Cycle 1 (including the Lead-in Period)

A subject is considered to have met the minimum exposure criterion at a dose level if the subject received PLD on Day 1 and 3 doses of VX 984 within 5 days with the first dose of VX-984 on Day 2. Subjects who do not have a DLT during Cycle 1 are considered to have sufficient safety evaluations if they have been observed through the end of Cycle 1 following the administration of PLD and VX-984, and are considered by both the sponsor and Investigators to have enough safety data to conclude that a DLT did not occur

- The Safety Set is defined as all subjects who received at least 1 dose of study drug. The Safety Set will be used for safety analyses
- The Full Analysis Set is defined as all subjects who received at least 1 cycle of study drug and have a baseline scan. The Full Analysis Set will be used for efficacy analyses.

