8.2 Definition of Analysis Sets

Screening Analysis Set (SCR)

The SCR includes all subjects who provided informed consent.

Safety Analysis Set (SAF)

The SAF will include all enrolled subjects who received at least 1 dose of study treatment. Analyses performed on the SAF will consider subjects as treated.

Dose-Limiting Toxicity Evaluable Set (DLT)

The DLT will include all subjects in the SAF who either meet the minimum exposure criterion and have sufficient safety evaluations (as determined by the Investigators and sponsor) or have had a DLT during Cycle 1.

Subjects who do not have a DLT during Cycle 1 will be excluded from the DLT Evaluable Set if the subject does not satisfy either of the following criteria:

Minimum exposure criterion

A subject is considered to have met the minimum exposure criterion at a dose level if the subject received PLD on Day 1, and 3 doses of VX-984 within 5 days with the first dose of VX-984 on Day 2.

Completion of Cycle 1

A subject is considered to have sufficient safety evaluations if the subject has been observed through the end of Cycle 1, which is defined as up to 28 days after the start of study treatment from Cycle 1.

Subjects who have been replaced by Safety Monitoring Committee decision will also be excluded from this analysis set.

Full Analysis Set (FAS)

The FAS will include all enrolled subjects who received at least 1 dose of study treatment.

As the FAS is identical to the SAF, the term FAS/SAF will be used to reflect that those analysis sets contain the same subjects.

Pharmacokinetic Analysis Set (PAS)

The PAS will include of all subjects who receive at least 1 dose of VX-984 or PLD and provide at least one measurable post-dose concentration of VX-984 or one measurable post-dose concentration of PLD. Subjects will be analyzed according to the actual treatment they received. All PK listings will be based on this analysis set.

Use of analysis sets is described in Table 2.

Table 2 Summary of Analysis and Associated Analysis Set

Analyses	SCR	FAS/SAF	DLT	PAS
Dispositions and deaths	✓			
Baseline Assessments		✓		
Past and Concomitant Therapies		✓		
Compliance and Exposure		✓		
Efficacy		✓		
Safety: MTD (Primary endpoint)			✓	
Safety and Tolerability		✓		
PK				✓

9 General Specifications for Data Analyses

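### The 3-dose exposure rule for DLT evaluability does not fit the reduced VX-984 schedules that the protocol permits: in a cohort planned with fewer than 3 doses, or with doses after Day 6, only subjects with a DLT could be evaluable

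*Protocol*

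**What the plan says.** Protocol 8.1.2.1.7 gives two routes to being evaluable for dose escalation. The first is exposure: "Subject must receive PLD on Day 1 and receive all 3 doses of VX-984 within 5 days (Days 2 to 6", with the first of those doses on Day 2. The second is toxicity: "The subject must have had a DLT during Cycle 1". Anyone who meets neither "will not be evaluable for dose escalation decisions and will be replaced".

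The same dose count defines the DLT Evaluable Set. Protocol 12.2 asks that a Part A subject "received PLD on Day 1 and 3 doses of VX 984 within 5 days". SAP 8.2 counts the exposure criterion as met "if the subject received PLD on Day 1, and 3 doses of VX-984 within 5 days with the first dose of VX-984 on Day 2". Neither adapts the count to a different schedule.

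Other parts of the protocol foresee a different schedule. Section 8.1.2.1.2 says that if three daily doses after PLD are not tolerated, "less frequent dosing of VX-984 may be explored in subsequent cohorts". Section 8.1.2.2 sets Part B dosing on Days 2 to 4 "unless in Part A the number of days was decreased due to tolerability". Sections 8.1.2.1.5 and 12.3.3.1 tie the MTD to a given schedule, cap its DLT rate at 33.3%, and base it on the DLT Evaluable Set. No reduced schedule is specified anywhere: the documents give neither a number of doses nor the days.

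**The concern.** An exposure criterion should remove subjects who did not receive the treatment planned for them. A fixed count does that only when the plan is three doses. If the plan is one or two, a fully compliant subject fails the exposure route by design, and only the toxicity route remains. Entry to the set then depends on the outcome that the set is meant to measure.

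The affected cohort would be the one opened because the 3-day schedule was not tolerated. Its purpose would be to show whether a lighter schedule is safer, and the rule would remove exactly the subjects who could show that. The same set feeds the Bayesian model (Protocol 12.3.3.1) and is the denominator of the DLT table for the MTD, a primary endpoint (SAP 15.1).

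**Working it through.** The plan has no figure of its own to reproduce here: Protocol 12.1 states that Part A has no power calculation. The check applies the rule literally.

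**Step 1. Which schedules can meet the rule?** The test is first dose on Day 2 and 3 doses within Days 2 to 6, assuming full compliance. Only the first row is in the documents; the others are illustrations.

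| VX-984 days in Cycle 1 | Doses within Days 2 to 6 | Rule met |
|---|---|---|
| 2, 3, 4 | 3 | yes |
| 2, 4, 6 | 3 | yes |
| 2, 4 | 2 | no |
| 2 | 1 | no |
| 2, 5, 8 | 2 | no |
| 2, 9, 16 | 1 | no |

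**Step 2. What rate is reported when the rule cannot be met?** With x DLTs among n compliant subjects, the evaluable number is x. The reported rate is x/x instead of x/n.

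| DLTs / treated | Compliant subjects counted | Rule as written |
|---|---|---|
| 0/3 | 0% | 0/0, undefined |
| 1/3 | 33.3% | 1/1 = 100% |
| 1/6 | 16.7% | 1/1 = 100% |
| 2/8 | 25.0% | 2/2 = 100% |

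The 2/8 counts are those of the example in Protocol 8.1.2.1.2. In the last three rows the rate moves from at or below the 33.3% cap to far above it.

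**Step 3. How often would the set be empty?** The chance is (1 − p)^n, where p is the true DLT rate. The documents give no p for a reduced schedule, so 0.10 to 0.333 is assumed.

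| p | n = 3 | n = 6 |
|---|---|---|
| 0.10 | 0.729 | 0.531 |
| 0.166 | 0.580 | 0.337 |
| 0.25 | 0.422 | 0.178 |
| 0.333 | 0.297 | 0.088 |

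**Step 4. What does replacement cost?** Each evaluable subject must have a DLT, so the mean number treated to obtain m evaluable subjects is m/p. For m = 3 this is 30, 18.1, 12 and 9 at the four rates. However, Protocol 8.1.2.1.2 stops enrolment to a cohort at 2 DLTs, so 3 evaluable subjects would not be reached. The mean number treated by the second DLT is 2/p: 2/0.10 = 20, 2/0.166 = 12.0, 2/0.25 = 8 and 2/0.333 = 6.0. Planned cohorts are 3 to 6 subjects, and all of Part A is about 50.

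**Step 5. Effect on overdose control.** The numerical prior of the model is not in the documents, so this uses a simple beta-binomial posterior for one dose as an illustration. With a Beta(1,1) prior, the probability that the DLT rate is at least 0.333 is 0.264 for 1/6 and 0.889 for 1/1; for 2/8 and 2/2 it is 0.378 and 0.963. With Beta(0.5,0.5) it is 0.200 for 1/6 and 0.908 for 1/1, so the dose passes the 25% limit on the full counts and fails it clearly on the counts as written.

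**The case against.** Several points weigh on the other side.

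- **Less frequent need not mean fewer.** Three doses spaced more widely, as on Days 2, 4 and 6, meet the rule. This stands and limits the scope. It does not remove the problem, because Protocol 8.1.2.2 itself speaks of a decreased number of days.
- **People decide, not the model.** Under Protocol 8.1.2.1.8 the sponsor and investigators review all toxicity data and must reach consensus, and 12.3.3.3 treats the model output as guidance. An unnoticed 100% rate driving a decision is unlikely. This softens the effect on decisions. It does not correct the model input or the DLT table, and overriding the rule would depart from the written definition.
- **The intent is clear.** Section 8.1.2.1.7 asks for all of the doses, which suggests the full planned course. That is probably the intent, but Protocol 12.2 and SAP 8.2 give only a bare count of 3.
- **A reduced schedule would have to be written down anyway.** Table 3-3 and its footnotes are fixed to Days 2 to 4, so the evaluability rule could be revised at that point. A reader might infer that such a cohort could open without an amendment. The documents do not say so either way.
- **The SAP may be looser.** It excludes a DLT-free subject who does not satisfy either criterion, which could be read as failing both. Its lead sentence requires exposure and sufficient safety evaluation together, as Protocol 12.2 does, and 8.1.2.1.7 would still exclude the subject.
- **The SAP runs no model.** Section 15.1 plans only a DLT count table and a listing, and SAP 13 describes only Days 2 to 4 dosing. This is right: the effect on the model comes from the protocol.

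**Conclusion.** The point holds in a limited and conditional form. Three sections fix the exposure criterion at 3 doses within 5 days, while two others allow schedules that cannot meet it. For a cohort planned with fewer than 3 doses, or with doses after Day 6, the DLT Evaluable Set contains only subjects with a DLT: 1 in 6 becomes 1/1, and no DLTs leaves the set empty. The rates in Steps 3 and 4 rest on an assumed p of 0.10 to 0.333, and those in Step 5 on assumed priors. The contradiction itself rests on the wording alone.

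Three stronger readings are tempting but unsupported. A reader might infer that every less frequent schedule is affected; Days 2, 4 and 6 is not. A reader might infer that the observed rate always becomes 100%; that needs at least one DLT. A reader might infer that replacement would never end; the 2-DLT stop would end it. The documents also do not say whether a reduced schedule was ever used. This is a minor point, but the rule is wrong as written for an option that the protocol permits.

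**What to change.** In Protocol 8.1.2.1.7, Protocol 12.2 and SAP 8.2, replace the fixed count and window with: PLD on Day 1 and all VX-984 doses planned for Cycle 1 under the cohort's assigned schedule, within a window defined for that schedule. Keep 3 doses within Days 2 to 6, starting on Day 2, as the definition for the 3-day schedule.

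The window must change along with the count. If the 5-day limit stayed for all schedules, dosing on Days 2, 5 and 8 would still exclude every DLT-free subject. Protocol 9.6 refers back to the evaluability section for replacement, so it follows without its own edit. In SAP 8.2, also state that a DLT-free subject must meet both the exposure and the observation criteria.

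The cost is one phrase in three places, plus setting a window if a reduced schedule is opened. Nothing changes for 3-day cohorts. This takes no position on which schedule should be used.

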## 8.1.2.1.8 Dose Escalation Process/Decision Making

At the end of each treatment cohort, the sponsor will convene a teleconference with the Investigators of the escalation phase. At the dose escalation teleconference, the clinical course (safety information including both DLTs and all CTCAE Grade ≥ 2 toxicity data during Cycle 1 as well as PK data) for each subject in the current dose cohort will be discussed. Updated safety data on other ongoing subjects, including data in later cycles, will be discussed as well.

Safety laboratory results and AEs occurring up to and including Day 28 of Cycle 1 will be reviewed as soon as they are available for a given cohort. Assessments for Day 28 of Cycle 1 must take place before dosing on Day 1 of Cycle 2. In this case, predose assessments on Day 1 of Cycle 2 will be used for DLT evaluation. DLTs that may have occurred through Day 28 of Cycle 1 of the current cohort, as well as DLTs that have occurred in prior cohorts in later cycles, will be identified.

To determine the dose regimen for the next cohort, the available toxicity information (including DLTs, AEs that are not DLTs, and AE information post-Cycle 1), PK, PD, and anti-tumor activity information, as well as the recommendations from the BLRM will be evaluated by the Investigators and sponsor study personnel (including the sponsor physician and statistician responsible for this study) at the dose decision meeting. The parties must reach a consensus on whether to declare MTD, escalate the dose any further, or whether to de-escalate and/or expand recruitment into particular cohorts.

## 8.1.2.1.9 Intra-Subject Dose Escalation

Intra-subject dose escalation is not permitted during the first 4 cycles of treatment. After the fourth cycle is completed, individual subjects may be considered for treatment at a dose of VX-984 in combination with PLD higher than the dose to which they were initially assigned. In order for a subject to be treated at a higher dose of VX-984 in combination with PLD, the subject must have received a lower dose for at least 4 cycles without a treatment-related or possibly-related toxicity of CTCAE Grade ≥ 2. Moreover, the new, higher dose with which the subject is to be treated must be a dose that has completed evaluation in a dose escalation meeting and that has not exceeded the MTD estimated by the BLRM. Any further increases after the initial intra-subject dose escalation will follow the same rules as for the initial intra-subject escalation. Consultation with the sponsor must occur before any intra-subject dose escalation decision.

## 8.1.2.2 Part B

During each cycle, subjects will be administered PLD on Day 1, and VX-984 will be dosed on Days 2 to 4 of a 28-day cycle unless in Part A the number of days was decreased due to tolerability. Treatment Period assessments are listed in Table 3-3. Approximately 40 subjects will receive VX-984 with PLD at the MTD or lower, as determined during the dose escalation phase.

Upon completion of the first cycle of treatment for at least 10 subjects within Part B, if the observed DLT rate exceeds 33.3%, the BLRM will be re-run to confirm that the estimated MTD still satisfies the overdose criteria of the model. If the dose fails to satisfy the criteria, a

change to the dose under study may be made according to the BLRM recommendation after review of the clinical data.

Subjects will continue to receive treatment until disease progression, unacceptable toxicities, or withdrawal of consent. Subjects will be evaluated by CT scans at the end of every 2 cycles for the first 6 cycles and every 2 to 3 cycles thereafter (see Table 3-3). If in the opinion of the Investigators, subjects may benefit with continued treatment with PLD and VX-984, subjects may continue to receive treatment beyond the total exposure of 550 mg/m² PLD. If there is evidence of progressive disease as determined using RECIST 1.1, treatment will be discontinued. In addition, subjects will be evaluated by transthoracic echocardiogram at baseline and at the end of every 2 cycles (see Table 3-3).

All subjects who meet the eligibility criteria and are administered at least 1 dose of VX-984 will be evaluable for safety. Subjects who meet the eligibility criteria, are administered at least 1 cycle of study drug, and have a baseline scan will be evaluated for efficacy. For subjects requiring palliative radiotherapy, irradiated lesions will be evaluable for progression, not response.

# 8.1.3 Stopping Rules (Parts A and B)

Subjects may be discontinued from study drug as follows:

- Subjects experiencing a non-reversible or life-threatening DLT may be discontinued from study drug at the Investigator's discretion, but will continue to complete follow-up assessments until documented progressive disease. Subjects who have a reversible and non-life threatening DLT and, in the judgment of the Investigator, may be exhibiting clinical benefit, may resume therapy after the toxicity has decreased to Grade < 2
- Subjects with progressive disease before the end of Cycle 1 may be discontinued from study drug at the discretion of the Investigator. Subjects with progressive disease beyond Cycle 1 will be discontinued from study drug. In cases where progression is not clear and in the opinion of the Investigator, the subject may be having clinical benefit, at the discretion of the Investigator, the subject may continue treatment but must be reimaged within 2 cycles of treatment
- For dose delays of more than 4 weeks due to drug-related toxicity other than Hand-Foot Syndrome (HFS) and stomatitis: Discontinue treatment, unless in the opinion of the Investigator, the subject is experiencing clinical benefit and it is in their best interest to continue treatment. For these subjects treatment may continue at a reduced dose at the discretion of the Investigator and sponsor
- Part A only: Exposure to PLD exceeds 550 mg/m^2.

# 8.1.4 Follow-up (Parts A and B)

All subjects, regardless of reason for discontinuation, will have a Safety Follow-up Visit  $28 (\pm 7)$  days following the last dose of study drug, during which the procedures listed in Table 3-3 will be completed. In addition, all subjects who receive all scheduled study drug doses through Cycle 1, have not had evidence of disease progression, and have not initiated

cancer therapy outside of the study protocol will have radiologic follow-up 5 weeks  $(\pm 1 \text{ week})$  after the last cycle of chemotherapy.

A survival follow-up assessment will be performed for all subjects at the last subject last visit for that part. For the survival follow-up assessment, every subject who is not known to have died during the course of the study will be called to ascertain whether the subject is alive, if the subject has initiated another therapy, or if the subject died. If the subject has initiated another therapy or died, the date of initiation of the other therapy or date of death will be confirmed.

Subjects in Part B who complete at least 6 cycles of treatment, discontinue for reasons other than disease progression, and do not have disease progression on the radiologic follow-up visit will be followed by staging CT scan (if possible) approximately every 8 weeks until disease progression, the subject starts a new line of therapy, the subject dies, the study closes, or the subject is at least 12 months from end of treatment, whichever comes first.

Finally, for Part B, regardless of disease progression or initiation of new line of therapy, subjects may be followed by telephone, electronic, or mail communication, or in person, every 3 months for up to 1 year or until the subject is lost to follow-up or dies, whichever occurs first

